By my signature below, I agree to conduct this Study in accordance with the Clinical Trial Protocol, current Good Clinical Practice (cGCP) and Good Laboratory Practice (cGLP) guidelines, obligations as set forth in Title 21 CFR Parts 812, 54, 5,6 and 11 (as applicable), and any applicable regulatory laws. I will make no changes to protocol-defined procedures without written permission from the Sponsor.

I understand that Investigational Use Products may be used **only** for the purposes explicitly described in this protocol.

I further agree to treat the results of this Study as confidential information and will not submit the results of the Study for publication without prior written authorization from the Sponsor.

[name]

PRINTED NAME

SIGNATURE

7/15/2021

DATE

SYNOPSIS

Title of Study	Phase I study to examine the safety and efficacy of allogeneic MSCs in suppressing inflammation in patients with small abdominal aortic aneurysm (AAA)
Objectives	Assess the safety and efficacy of systemic (IV) administration of escalating doses of allogeneic MSCs in modulating immune cell phenotypes and suppressing aortic inflammation in patients with small AAA.
Planned Number of Subjects and Duration of Involvement	36 patients
Patient Population	Abdominal aortic aneurysms (AAA) patients
Investigational Product Name	Allogeneic mesenchymal stem cells
Methodology Overview	In a double blind, Phase I trial, 36 patients with AAA measuring 30-50mm in maximal transverse diameter (MTD) will be randomized in a 1:1:1 fashion to receive either 1.0×10^6 MSCs/kg (n=12), 3.0×10^6 MSCs/kg. (n=12), or placebo (Plasmalyte A) (n=12) delivered intravenously. The primary safety endpoints will be incidence of treatment related adverse events at 24 months post MSC-administration. Exploratory primary efficacy endpoints will be changes in circulating inflammatory cell phenotypes and aortic inflammation as measured by CT. The treatment period will involve long-term follow-up through 5 years. The incidence of surgical intervention, aneurysm related death, quality of life, and major adverse cardiac events will be recorded.

Table 1 Abbreviations

AAA	Abdominal Aortic Aneurysm
AE	Adverse Event
AMI	Acute Myocardial Infarction
ASC	Adipose derived MSC
bMSC	Bone marrow derived MSC
CTSI	Clinical and Translational Sciences Institute
DSMB	Data Safety Monitoring Board
eGFR	Effective Glomerular Filtration Rate
GVHD	Graft Versus Host Disease
IFN- γ	Interferon- γ ,
IL	Interleukin

12.2 Case Report Forms/Electronic Data Records	26
12.3 Access to Source Documents	26
12.4 Financial Disclosure	27
12.5 Deviations from the Study Protocol	27
12.6 Record Retention	27
12.7 Publication Policy	27
13. ETHICS AND COMPLIANCE	27
13.1 Informed Consent and De-Identification	27
13.1.1 Prospectively Collected Data	27
13.2 IRB Review	28
13.3 Confidentiality of Data and Patient Records	28
13.3.1 Provisions to Protect the Privacy Interests of Participants	28
14. REFERENCES	289

2. INTRODUCTION.

Each year 200,000 people are diagnosed with AAA in the U.S. and 15,000 will inevitably die from rupture.¹ Approximately 39,000 endovascular or open surgeries are performed annually to prevent complications of AAA with two-year costs of \$105,745 and \$108,344 (2012 U.S. dollars), respectively.² The risk of rupture accelerates with AAA diameter thus an effective therapy that could mitigate AAA expansion would have a significant impact on patient survival, quality of life, and health care costs. In a recent randomized, placebo-controlled trial; doxycycline, an inhibitor of a key protease implicated in AAA formation, matrix metalloproteinase-9 (MMP), failed to reduce AAA expansion.³ The pathogenesis of AAA begins with early T-cell and macrophage activation with subsequent recruitment of neutrophils and activation of MMPs.¹ The result is smooth muscle cell apoptosis, elastin degradation, and loss of structural integrity of the aortic wall. Extinguishing this inflammatory cascade in its initiation may prove more effective than targeting later phase proteases.

Mesenchymal stromal cells (MSC) have pleiotropic immunomodulatory properties relevant to the pathogenesis of AAA.^{4,5} Our laboratory has shown that MSCs induce formation of immunosuppressive T-regulatory cells, decrease cytotoxic CD28-T cells, promote polarization of macrophages to the anti-inflammatory M2 phenotype, and inhibit neutrophil infiltration. Furthermore, human MSCs delivered intra-venously significantly decreased AAA inflammation and expansion in murine models, evidence that MSCs warrant further evaluation for this purpose in the context of a clinical trial.⁶

The objective of this study is to conduct a single center, double blind, Phase I trial to test the safety of systemic (intravenous, IV) administration of allogeneic bone marrow derived MSCs and compare two doses (1 million and 3 million MSCs/kg. in modulating inflammatory responses in patients with small AAA. The rationale for this investigation is: (1), there are no effective treatment options that suppress AAA inflammation and expansion; (2), there is an established safety profile of MSCs in previous clinical trials⁷⁻¹¹; and (3), compelling preliminary data supporting this concept.

3. DESCRIPTION OF THE INVESTIGATIONAL PRODUCT

3.1 Overview

[figure not shown]
Human bone marrow derived MSCs increase T- regulatory (Treg) cells and decrease CD4+ and CD8+ cytotoxic T-cells in co-culture with peripheral blood mononuclear cells collected from AAA patients. Furthermore, we have demonstrated that human MSCs increase Tregs in blood and aortic tissue in mouse models of AAA while significantly decreasing aneurysm expansion. Treg induction presents a novel approach that may clinically suppress the inflammatory processes pathogenic in AAA formation.

3.2 Preclinical Data using adult human allogeneic bone marrow derived MSCs to support this IND.

[figure not shown]
3.2.1 The allogeneic MSCs used for these experiments are provided by Case Western Reserve University in Cleveland, Ohio. MSCs were obtained from 50 mL of bone marrow aspirated from a young, healthy donor. Mononuclear cells were cultured in 175 cm² flasks. Adherent cells were harvested and passaged (P1) into new flasks and at 70-80% confluence, they were further expanded to a second passage only (P2). MSCs used in these preclinical studies were manufactured using the exact processes that will be used for the MSCs to be used in the clinical trial detailed in this IND, thus we expect that MSC potency will be equivalent.

3.2.2 Circulating CD4⁺FoxP3⁺ T-regulatory cells are decreased in patients with AAA and significantly increased after co-culture with Human MSCs. PBMC specimens were isolated from patients undergoing endovascular AAA repair (n=10) and healthy subjects (n=5) and were stained with fluorochrome labeled

antibodies for CD3, CD4, CD25, and after permeabilization, for FoxP3, as previously described.⁹ We found that there were significantly fewer circulating Treg cells in AAA patients ($0.46 \pm 0.07\%$) as compared to healthy controls ($0.67 \pm 0.16\%$, $P=0.01$), (Fig.1A). PBMCs from AAA patients were then co-cultured with MSCs or saline for 7 Days and Treg were then quantified with FACS. MSCs significantly increased Treg at 7 days compared to control ($2.56 \pm 0.06\%$ vs. $1.07 \pm 0.04\%$, $P < 0.01$) (Fig. 1B, C).

[figure not shown]

3.2.3 Human MSCs increase T-regulatory cells in aortic aneurysm tissue in the mouse elastase AAA model. C57Bl/6 mice were given hMSCs (1×10^6) or PBS 24 hours after aortic elastase perfusion. Mice were sacrificed at Days 1, 4, and 7 and aortas harvested. Immunohistochemical (IHC) staining of aneurysm sections (Fig. 2A) demonstrated that hMSCs significantly increased murine Treg as compared to controls at each time point (Fig. 2B).

[figure not shown]

3.2.4 Human MSCs increase immune suppressor function in the mouse elastase AAA model. Using the murine elastase AAA model, 1×10^6 human MSCs or phosphate buffered saline (control) were injected IV ($n=5$ /group) at the time of elastase application. At 72 hours the mice were sacrificed and CD4⁺CD25⁺ cells were isolated from PBMC using magnetic beads followed by cell sorting to isolate Tregs

(CD4⁺CD25⁺CD127^{lo}) and CD4⁺CD25⁺ T-cells (responder cells). The cells were cultured in varying ratios: Treg: Tresp of 0.1:1.0; 0.5:1.0; and 1:1, in 96 well culture plates coated with 100 μ L of 5.0 μ g/mL anti-CD3 and anti-CD28. Controls were the CD4⁺CD25⁻ responder cells plated alone. Cell proliferation was measured using a modified 3-[4,5-dimethyl-2-thiazol-yl]-2,5-diphenyltetrazolium bromide assay with a Premix WST-1 Cell Proliferation Assay System as described. Percentage suppression was determined at each ratio of Treg: Tresp by comparison with CD4⁺CD25⁻ cells (Tresp) plated alone. We found that immunosuppressive activity was significantly increased in Tregs from MSC treated compared to control treated mice (**Fig. 3**).

3.2.5 Circulating CD4⁺CD28⁻ and CD8⁺CD28⁻ T-cells are increased in patients with AAA and significantly decreased after human MSC infusion in the murine elastase AAA model. The mononuclear cell fraction of peripheral blood (PBMC) was isolated from patients with AAA and age matched healthy subjects and analyzed with FACS. Percentages of CD4⁺CD28⁻ and CD8⁺CD28⁻ T-cells were significantly greater in AAA patients compared with healthy controls. Adjusting for normal accumulation of CD28⁻ T cells in healthy controls, 60.4% of the AAA patients had elevated levels of CD4⁺CD28⁻ T cells and 19.8% showed increased levels of CD8⁺CD28⁻ T cells in the peripheral blood (**Fig.4 A**). MSCs or phosphate buffered saline (PBS) were infused in C57Bl6 mice at the time of AAA induction. CD4⁺CD28⁻ and CD8⁺CD28⁻ T-cells and Neutrophils (Ly6G/C⁺) from aortic aneurysm tissue specimens were quantified using flow cytometry at Day 7 after MSC or PBS infusion revealing a significant decrease in all of these pathogenic inflammatory cell phenotypes (**Fig.4B**).

3.2.6 Human MSCs preserve elastin and collagen and inhibit matrix metalloproteinase-9 activity in the murine elastase AAA model. Using the topical elastase AAA model, we performed histological comparisons of the aneurysmal tissue to assess the effects of MSCs on elastin and collagen fiber content in the extra-cellular matrix of the aortic wall. We found that compared to control mice, MSC treated mice retained elastin lamellae and collagen fibers (**Fig. 5A-C**). Elastin is the primary architectural protein of the aorta and is destroyed by production of MMP-9 by activated inflammatory cells leading to loss of tensile strength and aneurysm formation. MMP-9 serum levels are elevated in about 50-70% of patients with AAA. MSCs have been shown to secrete tissue inhibitors of metalloproteinase-1 and -2 that inhibit MMP-2 and -9 activity *in vitro*. We found that compared to control treated AAA mice, MSCs significantly decrease serum MMP-9 activity (**Fig. 5D**).

[figure not shown]

Figure 5. Representative images after staining fixed sections of the murine aorta 14 days after aneurysm induction (40x magnification). Hematoxylin and Eosin staining reveals preservation of the tunica media in MSC treated compared to phosphate buffered saline treated mice (**A**), MSC treated mice showed reduced aortic elastin fragmentation (**B**), and collagen degradation (**C**). Using the *Anaspec Sensolyte* MMP-9 assay kit MMP activity was measured in relative fluorescence units at Ex/Em 490/520, as previously described. MMP-9 activity was significantly decreased compared to PBS treated mice at Day 3 (365.54 ± 21.76 RFU SEM vs 501.66 ± 40.51 RFU SEM, $p < 0.05$) and at Day 14 (295.13 ± 77.89 RFU SEM vs 805.56 ± 76.53 RFU SEM, $p < 0.05$), with a trend towards decreased MMP-9 activity at Day 7 ($p = 0.8$) (**D**).

3.2.7 Systemic infusion of human MSCs suppresses IL-17, -23, and IFN- γ and AAA expansion in the mouse elastase model. We delivered hMSC IV on day 1 after perfusion of the aorta with elastase. We then measured aortic diameter by video micrometry at Day 14. Compared to baseline, aortic diameter was significantly decreased in hMSC-treated compared with saline treated mice (**Fig. 6A**).

[figure not shown]

Figure 6. Human bone marrow MSCs attenuate AAA expansion in the murine elastase model. MSCs significantly suppressed murine elastase induced aortic expansion by day 4 compared to vehicle (**A**). Mouse aorta ultrasound images of at baseline and days 4, 7 and 14 post elastase treatment or 1×10^6 human MSCs (i.v.) (**B**). $N=4-10/\text{group}$, $**p<0.01$.

3.2.8 IL-10 responses are deficient in AAA patients and robustly enhanced after MSC administration *in vivo* in the murine elastase AAA model. Serum levels of the anti-inflammatory cytokine IL-10 are significantly decreased in patients with AAA as compared to risk factor matched subjects without AAA, whereas as serum levels of TSG-6 and PGE₂ are increased in AAA patients. *This suggests that an impaired host IL-10 response to tissue injury and inflammation may contribute to AAA formation (Fig. 7).* Clinical grade MSCs exposed to TNF- α in culture robustly secreted 12x the levels of IL-10, 7.6x levels of TSG-6, 3.6x levels PGE₂, and 1.6x levels of TGF- β from unstimulated conditions (**Fig. 8A**). Using the same MSC stock we then administered 1×10^6 cells to our mouse AAA model. Using species specific antibodies for human and mouse IL-10 we discovered that mouse serum levels of human IL-10 peaked at Day 3 and then were undetectable by Day 7. Serum levels of mouse IL-10 were significantly increased at Day 7 and continued to increase to Day 21 (when the experiment was terminated) in MSC treated treated AAA mice (**Fig. 8B**). Thus it appears that MSCs induce a delayed endogenous host IL-10 response that may sustain the anti-inflammatory effect after human MSCs are cleared. Tr1 regulatory cells are induced by exogenous IL-10 and exert immunoregulatory control via secretion of IL-10. Thus we plan to enumerate Tr1 in addition to FoxP3⁺ Tregulatory cells in Aim 1 of this proposal.

[figure not shown]

Figure 7. IL-10 is deficient in patients with AAA. Blood samples were collected from patients being screened AAA. Using the Bio-plex multi-analyte system we found significant differences in, IL-10 (14.36 ± 0.51 vs. 8.03 ± 1.01), IL-17a (9.00 ± 4.16 vs. 67.82 ± 32.93), IFN- γ (3.22 ± 1.69 vs. 40.63 ± 17.66), TNF- α (5.14 ± 1.84 vs. 8.32 ± 0.99), PGE $_2$ (54.3 ± 21.02 vs. 176.69 ± 43.1), and TSG-6 (545.8 ± 358 vs. 9826.53 ± 1280), pg./ml; non-AAA vs. AAA, respectively, $P < 0.01$

[figure not shown]

Figure 8. Mesenchymal Stromal Cells robustly secrete IL-10 *in vitro* and induce an endogenous IL-10 response *in vivo*. MSCs were cultured to 90% confluency and 10ng/ml of TNF- α was added. After 24 hours the supernatant was collected and analyzed by ELISA. IL-10 increased from 1.12 ± 0.31 to 13.23 ± 0.25 pg/ml, TGF- β \uparrow 148.08 ± 11.29 to 245.12 ± 19.74 pg/ml., PGE $_2$ \uparrow from 704.12 ± 21.2 to 2586.52 ± 142.69 ng./ml., and TSG-6 \uparrow from 1474.82 ± 11.41 to 11276.06 ± 1802.06 ng./ml. (\pm SEM) (A). Using our murine elastase model we administered 1×10^6 human MSCs after AAA induction and peripheral blood ($n=5$ /per time point) was collected. Using ELISA with species specific antibodies we found that there was an initial surge of human IL-10 peaking at Day 3 (25.59 ± 11.11 pg./ml) and undetectable at Day 7. Murine IL-10 significantly increased at Day 7 (148.63 ± 23.62 SEM pg./ml) in MSC treated mice vs. control (73.71 ± 12.02 pg./ml.) and peaked at Day 21 (426.28 ± 21.52 pg./ml) vs. control (69.21 ± 19 pg./ml), when the experiment was terminated. (\pm SEM) * $P < 0.05$, ** $P < 0.01$, and *** $P < 0.001$ compared to control (B).

3.3 Proposed Intended Use Statement

Allogeneic MSCs are a novel therapeutic option to suppress growth of small AAA. Human MSCs are intended for investigational use only by selected investigators familiar with their use and experienced in conducting clinical studies. Human MSCs may only be administered to human subjects participating in clinical studies sponsored/approved by Indiana University School of Medicine, and who have provided formal written consent.

3.4 Study Objectives.

The principal objective of this study is as follows:

Assess the safety and efficacy of administration of allogeneic MSCs in patients with small AAA.

This study will test the hypothesis that administration of MSCs in doses of 1×10^6 MSCs/kg. and 3×10^6 MSCs/kg demonstrate safety in patients with small AAA. This trial will also test the hypothesis that MSCs, in a dose dependent fashion (1×10^6 MSC/kg. vs. 3.0×10^6 MSC/kg.), promote the frequency and immune suppressor function of Treg cells and decrease AAA inflammation as measured by computed tomography. In an double blinded, Phase I trial, 36 patients with AAA measuring 35-50 mm in maximal transverse diameter (MTD) will be randomized in a 1:1:1 fashion to receive intra-venously either a single dose of 1×10^6 MSCs/kg., 3×10^6 MSCs/kg. , or placebo (Plasmalyte A) (n =12/group). The primary safety endpoints will be incidence of treatment related adverse events accrued over 24 months. Efficacy measures are changes in frequency and immune suppressor function of Tregs, number and cytotoxic activity of CD4+/CD8+ CD28- T-cells, activated monocytes, and changes in aortic inflammation as measured by PET CT compared to baseline. Secondary endpoints measured out to year 5 will include changes in IL-10 and Tr1 levels. Duplex ultrasound measurements of the AAA, which is considered standard of care, will be recorded as change in aortic inflammation during long-term follow-up. Incidence of surgical intervention, aneurysm related death, quality of life, and major adverse cardiac events will be recorded through year five (5).

Completion of this study will determine if MSCs are safe in patients with AAA and provide critical insights that will direct a placebo-controlled, Phase II randomized trial.

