5. STUDY POPULATION

5.1 Sample Size and Target Study Population

5.1.1 Sample size

The total number of individual subjects is expected to reach up to 36.

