9. STATISTICAL METHODS

The safety of systemic administration of allogeneic MSCs will be measured by treatment-related adverse events. Treatment-related adverse events will be categorized by overlapping systems and severities. The three categories of systems are cardiovascular, respiratory, or infectious. Two categories of severity will be serious adverse (SAE) and major adverse cardiac events (MACE). For completeness, instances of adverse events may appear in more than one category. Within each of these categories adverse events will be listed in descending order of frequency for the treatment-group. In addition, for each category, the sum and difference between the two routes of delivery of the proportions will be reported as percent incidence. Confidence Intervals at the 95% confidence level and *P*-values for these four groups will be calculated. Since four previous trials have not reported adverse events with MSC treatment, confidence intervals will be generated by the method of the Wilson Score Interval because they are robust, with good coverage probability even for small number of trials and are not degenerate near zero. These intervals will be used to summarize the data rather than as any formal inferential statement. No adjustment for multiplicity will be made.

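### Section 3.4 says the trial will test and determine the safety of MSCs, but the plan supports only an estimate of incidence, with a 95% upper limit of 24.2% per dose arm even if no event occurs

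*Combined protocol and SAP*

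**What the plan says.** Section 3.4 (Study Objectives) labels its principal objective as assessing the safety and efficacy of MSCs. Two later sentences go further. One reads "This study will test the hypothesis that administration of MSCs in doses of" 1 and 3 million cells/kg demonstrates safety. The other reads "Completion of this study will determine if MSCs are safe in patients with AAA", and goes on to say that the trial will inform a randomised, placebo-controlled Phase II study.

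The endpoint is stated in the same section: "The primary safety endpoints will be incidence of treatment related adverse events accrued over 24 months". Patients are allocated 1:1:1 to two MSC doses "or placebo (Plasmalyte A) (n =12/group"). Section 5.1.1 gives the sample size without a rationale: "The total number of individual subjects is expected to reach up to 36".

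Section 9 (Statistical Methods) plans "Confidence Intervals at the 95% confidence level" for adverse event proportions by the Wilson score method. It says of them: "These intervals will be used to summarize the data rather than as any formal inferential statement". There is no multiplicity adjustment. The same paragraph plans P-values, but for four groups, and a sum and difference of proportions over two routes of delivery. The trial has three arms and one route, intravenous. Section 9.2 limits the study report to summary analyses of safety and efficacy. Section 10.1 lists events that stop enrolment and prompt a review.

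**The concern.** A test of safety needs a rate or margin to test against and a rule for deciding. A determination of safety needs at least the rule. Section 3.4 promises both, and no section supplies either.

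The gap matters most for the result the plan expects. Section 9 chooses the Wilson method because four earlier MSC trials reported no adverse events, so low or zero counts are anticipated. An empty event table read alongside section 3.4 could pass for established safety, although sizeable event rates would remain compatible with it. Section 3.4 also says that this trial will guide the Phase II design.

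**Working it through.** **1. Is there a safety test anywhere in the plan?** Four places could supply one.

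- Section 9, intervals: expressly a summary and not formal inference.
- Section 9, P-values: attached to four groups in a three-arm trial, with no null hypothesis stated. They cannot be matched to the section 3.4 hypothesis.
- Section 9.2: summary analyses only.
- Section 10.1, stopping rules: each triggers a halt and review. Nothing says that not reaching them counts as evidence of safety.

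No section gives an acceptable rate, a margin, a power figure or a precision target. The stated 36 agrees with 3 × 12, but there is no power calculation to reproduce.

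**2. What can the planned interval show at best?** Inputs: n = 12 per arm and 2 × 12 = 24 on MSC (section 3.4); 95% Wilson (section 9). Sidedness is not stated, so two-sided is assumed and one-sided is shown as a variant. Incidence is taken as the proportion of patients with an event, with all patients followed to month 24.

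With zero events the Wilson upper limit is z²/(n + z²).

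| Result | Two-sided 95% (z² = 3.8415) | One-sided 95% (z² = 2.7055) |
|---|---|---|
| 0/12 | 3.8415/15.8415 = 24.2% | 2.7055/14.7055 = 18.4% |
| 0/24 | 3.8415/27.8415 = 13.8% | 2.7055/26.7055 = 10.1% |

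The exact (Clopper-Pearson) limit for 0/12 is 1 − 0.025^(1/12) = 26.5% two-sided and 1 − 0.05^(1/12) = 22.1% one-sided.

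**3. What if events occur?** The two-sided Wilson upper limit rises to 35.4% at 1/12 and 44.8% at 2/12. In the pooled group it rises to 20.2% at 1/24 and 25.8% at 2/24.

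**4. How often would a real risk produce no events?** The chance is (1 − p)^n.

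| True rate | n = 12 | n = 24 |
|---|---|---|
| 5% | 54% | 29% |
| 10% | 28% | 8.0% |
| 20% | 6.9% | 0.5% |

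**5. What does the comparison with placebo add?** An interval for the difference built from the Wilson limits (Newcombe) runs from −24.2 to +24.2 percentage points for 0/12 against 0/12. For 0/24 pooled against 0/12 it runs from −24.2 to +13.8 points. If the planned P-values were read as two-sided Fisher tests of one dose against placebo with no placebo events, p < 0.05 would need at least 5/12 on MSC (5/12: p = 0.037; 4/12: p = 0.093).

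**6. What would exclude lower rates?** With no events, the two-sided Wilson limit falls to rate r when n ≥ z²(1 − r)/r. For 10% that is 3.8415 × 0.9/0.1 = 34.6, so 35 patients. For 5% it is 3.8415 × 0.95/0.05 = 72.99, so 73. These figures show scale only; they are not a request to enlarge the trial.

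**The case against.** The best defence is that the operative plan is already modest. The labelled objective is only to assess safety, the endpoint is an incidence, and it has an interval. Twelve per arm with descriptive safety is ordinary in Phase I, and hypothesis may be meant there in its loose scientific sense. All of this stands. It confines the fault to two sentences in section 3.4, but does not make those sentences true.

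A reader might draw four stronger conclusions that the documents do not support.

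- **That a trial with no events would be reported as proof of safety.** Nothing says so. Section 9.2 promises summaries, and under section 9 a 0/12 result would carry its interval. The risk of misreading is an inference from the wording of section 3.4.
- **That the design cannot exclude a 24% rate in any sense.** The 24.2% figure is per arm, two-sided and for zero events. At a true rate of 24%, zero of 12 has probability 0.76^12 = 3.7%, so one-sided 95% limits (18.4% Wilson, 22.1% exact) would exclude it. The pooled 0/24 limit of 13.8% excludes it too, although the hypothesis is stated for each dose.
- **That section 9 rules out all inference.** The disclaimer covers the intervals. P-values are also planned; they simply have no hypothesis attached.
- **That the sample size is wrong.** No target is stated against which 36 could fail.

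The sum of proportions in section 9 might also be taken as a pooled MSC summary. It is defined over two delivery routes that this trial does not have, so it does not provide one as written.

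**Conclusion.** The point holds as a mismatch between the claim and the plan. Two sentences in section 3.4 promise a tested and determined safety conclusion, and the analysis provides a descriptive incidence with no criterion for safety. Best-case precision is an upper limit of 24.2% per arm and 13.8% in the pooled MSC group, and any event makes it worse.

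These figures assume two-sided 95% limits, zero events and complete follow-up of 12 patients per arm. Loss before month 24 would widen them. Zero is a favourable case, because section 11.1 itself lists rash, mild fever and myalgia as possible, if rare, reactions. The absence of a safety criterion does not depend on any of these assumptions. The point does not call for a larger trial or a formal safety test.

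**What to change.** **Section 3.4.** Keep the principal objective of assessing safety. Replace the two stronger sentences with wording such as:

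> The study will estimate the 24-month incidence of treatment-related adverse events in each arm and in the two MSC arms combined. If no events occur, the two-sided 95% Wilson upper limits will be 24.2% for an arm of 12 and 13.8% for the 24 MSC patients combined; any event will raise these limits.

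The part of the closing sentence about informing Phase II can stay.

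**Section 9, safety paragraph.** State that the limits are two-sided. Replace the sum and difference over delivery routes, and the reference to four groups, with:

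- Wilson intervals for each of the three randomised arms and for the pooled MSC group (n = 24);
- an interval for the MSC-minus-placebo difference, with a note that it spans about ±24 percentage points at 0/12 against 0/12.

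Either drop the P-values or name the comparison each one tests and label it descriptive.

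**Cost.** A less favourable stated claim and a few extra intervals. Sample size, visits, dosing and data collection do not change.
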